#### **6 month study:**

Patients must meet all inclusion and exclusion criteria for the short-term study, plus have poorly controlled diabetes, defined as a hemoglobin A1c  $\geq 7\%$ .

## **Study Design and Statistical Analysis**

### **Design**

This is a prospective, non-randomized study.

### **Randomization**

Although the optimal method to study short-term effects of thyroid hormone would be a randomized, double-blinded, placebo controlled, cross-over study, such a study design is not feasible in this population. This study design would require subjects to be hospitalized for more than 4 weeks (>2 weeks for each study period), and is unlikely to accrue sufficient subjects for successful completion in this extremely rare condition.

### **Outcome Measures**

The primary aim of this study is to determine the effect of thyroid hormone on glucose disposal over 2 weeks and A1c over 6 months in patients with mutations of the insulin receptor. In addition to quantification of glucose disposal, we plan to study effects of thyroid hormone on energy expenditure, substrate utilization, sympathetic nervous system tone, and gene expression in adipose tissue and muscle.

- **Primary outcome:**
  - **2 week intervention:** Total body glucose disposal in the fasting state measured using isotopic tracers
  - **6 month intervention:** Hemoglobin A1c

- **Secondary outcomes:**
  - **2 week intervention:**
    - Glycemic outcomes:
      - Tissue-specific glucose disposal in the fasting state in BAT, WAT, and muscle quantified using positron emission tomography (PET) in adults only
      - Glucose area under the curve measured using 7 point daily plasma glucose measurement, continuous interstitial fluid glucose monitoring, and oral glucose tolerance testing
      - Integrated assessment of glycemia over 2 weeks using hemoglobin A1c, fructosamine, and glycated albumin
      - Quantification of fractional gluconeogenesis and glycogenolysis using isotopic tracers
    - Energy Intake/Expenditure:
      - Resting energy expenditure at thermoneutrality (measured at 25-27 °C using indirect calorimetry in the metabolic chamber)
      - Core and peripheral body temperature
      - Food intake measurement
    - Gene expression in WAT and muscle biopsies in adults only
  - **6 month intervention:**
    - Glycemic outcomes:
      - Tissue-specific glucose disposal in the fasting state in BAT, WAT, and muscle quantified using positron emission tomography (PET) in adults only
      - Total body glucose disposal in the fasting state measured using isotopic tracers
      - Quantification of fractional gluconeogenesis and glycogenolysis using isotopic tracers
      - Glucose area under the curve measured using 7 point daily plasma glucose measurement, continuous interstitial fluid glucose monitoring, and oral glucose tolerance testing
      - Total daily dose of insulin
    - Energy Expenditure:
      - Resting energy expenditure at thermoneutrality (measured using indirect calorimetry in the metabolic chamber)
      - Core and peripheral body temperature
      - Food intake measurement

## Statistical Considerations

### Sample Size Justification

#### *2 week study*

The primary objective of the 2 week study is to assess the impact determine the effect of thyroid hormone on total body glucose disposal over 2 weeks in patients with mutations of the insulin receptor. Sample size is determined by the change in glucose disposal.

The null hypothesis is that the glucose disposal before and after thyroid hormone treatment is same.

The alternative hypothesis is that the glucose disposal is changed after the treatment

The sample size is calculated based on previous studies in literature. A similar study by Dimitriadis et al reported a difference in total body glucose uptake between the euthyroid and hyperthyroid conditions of  $0.39 \text{ mg}\cdot\text{kg}^{-1}\cdot\text{min}^{-1}$  with a standard deviation of  $<0.27$ . With this mean change and SD, a sample size of only 6 subjects would give 80% power with a two-sided alpha of 0.05 for this outcome. Based on the assumption that results for this study will fall in a similar ranges as those published in the literature, we calculate the sample size dependent on the glucose disposal change and its standard deviation, which are given in the following table.

| Glucose disposal change | Power=80% |        |        |        |        | Power=90% |        |        |        |        |
|-------------------------|-----------|--------|--------|--------|--------|-----------|--------|--------|--------|--------|
|                         | SD=0.1    | SD=0.2 | SD=0.3 | SD=0.4 | SD=0.5 | SD=0.1    | SD=0.2 | SD=0.3 | SD=0.4 | SD=0.5 |
| 0.2                     | 5         | 10     | 20     | 34     | 52     | 5         | 13     | 26     | 44     | 68     |
| 0.3                     | 4         | 6      | 10     | 16     | 24     | 4         | 7      | 13     | 21     | 32     |
| 0.4                     | 3         | 5      | 7      | 10     | 15     | 3         | 5      | 9      | 13     | 19     |
| 0.5                     | 3         | 4      | 6      | 8      | 10     | 3         | 5      | 7      | 9      | 13     |

Here we note that the sample size determined is only for studying the hypothesis about the primary response, total body glucose disposal. An additional power analysis was performed for a key secondary endpoint: the change in muscle glucose uptake on PET. Lahesmaa et al reported that the difference in muscle glucose uptake in the euthyroid versus hyperthyroid condition was 1.4 with a standard deviation of 0.6. With this mean change and SD, a sample size of only 4 subjects would give 80% power with a two-sided alpha of 0.05 for this outcome. Sample sizes for similar results are shown in the following table. For example, a sample size of 10 for this two treatment crossover study will have a probability of 80% to detect a change of glucose disposal 1.0 with standard deviation of 1.0 at a two sided 5% significance level.

| Glucose disposal change | Power=80% |        |        |        |        | Power=90% |        |        |        |        |
|-------------------------|-----------|--------|--------|--------|--------|-----------|--------|--------|--------|--------|
|                         | SD=0.4    | SD=0.6 | SD=0.8 | SD=1.0 | SD=1.2 | SD=0.4    | SD=0.6 | SD=0.8 | SD=1.0 | SD=1.2 |
| 0.5                     | 8         | 14     | 23     | 34     | 48     | 9         | 18     | 29     | 44     | 63     |
| 1.0                     | 4         | 6      | 8      | 10     | 14     | 5         | 7      | 9      | 13     | 18     |
| 1.5                     | 3         | 4      | 5      | 6      | 8      | 4         | 5      | 6      | 7      | 9      |

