The role of thyroid hormone excess in glucose metabolism has been investigated in several studies in humans with normal insulin receptor function. In general, patients with hyperthyroidism have *increased* blood glucose in the fasting and post-prandial states. This worsening of glucose metabolism appears to be due to worsening of post-receptor insulin resistance, particularly at the level of the liver, resulting in increased hepatic glucose production. In contrast, hyperthyroid patients (compared to euthyroid controls) have a 3-fold increase in glucose uptake in BAT, and 1.9-fold increase in glucose uptake in muscle; these normalize once patients return to a euthyroid state.

Recently, Lahesmaa et. al., reported that BAT takes up  $2.7 \pm 2.3$   $\mu\text{mol}/100\text{g}/\text{min}$  of glucose in the hyperthyroid state, and takes up  $0.9 \pm 0.1$   $\mu\text{mol}/100\text{g}/\text{min}$  of glucose in the euthyroid state. They also showed that in the hyperthyroid state, skeletal muscle takes up  $1.9 \pm 0.6$   $\mu\text{mol}/100\text{g}/\text{min}$  of glucose, and in the euthyroid state, takes up  $1.0 \pm 0.3$   $\mu\text{mol}/100\text{g}/\text{min}$  of glucose. If we assume that an average human possesses  $\sim 50\text{g}$  of BAT, and  $\sim 30,000\text{g}$  of muscle, then BAT will take up an excess of  $0.9$   $\mu\text{mol}/\text{minute}$  of glucose in the hyperthyroid vs. the euthyroid state, and muscle will take up an excess of  $270$   $\mu\text{mol}/\text{minute}$  of glucose in the hyperthyroid vs. the euthyroid state. Thus, muscle is anticipated to be the major organ taking up excess glucose in the presence of T3 treatment.

Taken together, these data suggest that, in patients with fixed insulin resistance due to insulin receptor mutations, thyroid hormone might enhance glucose disposal without worsening insulin resistance, resulting in a net improvement in glucose homeostasis.

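### The protocol gives two muscle glucose uptake differences for the same cited PET study (0.9 and 1.4), and the statement that 4 subjects give 80% power uses the unexplained 1.4

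*Combined protocol and SAP*

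**What the plan says.** Under Statistical Considerations, Sample Size Justification, 2 week study, the protocol states: "An additional power analysis was performed for a key secondary endpoint: the change in muscle glucose uptake on PET". For the inputs it relies on the cited PET study of hyperthyroid patients (reference 16): "the difference in muscle glucose uptake in the euthyroid versus hyperthyroid condition was 1.4 with a standard deviation of 0.6", without units. It concludes that "a sample size of only 4 subjects would give 80% power with a two-sided alpha of 0.05", and a grid of alternatives follows for changes of 0.5, 1.0 and 1.5 and SDs of 0.4 to 1.2.

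The same study is summarised in the Introduction, under Role of thyroid hormone in glucose uptake. The sentence beginning "They also showed that in the hyperthyroid state, skeletal muscle takes up" gives 1.9 ± 0.6 µmol/100g/min in the hyperthyroid state and 1.0 ± 0.3 in the euthyroid state. From these figures and an assumed 30,000 g of muscle, the Introduction derives an excess uptake of 270 µmol/min. Just before that, it describes hyperthyroid patients compared with euthyroid controls as having a "1.9-fold increase in glucose uptake in muscle; these normalize once patients return to a euthyroid state".

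The Sample Size Justification also limits what this calculation is for: "the sample size determined is only for studying the hypothesis about the primary response, total body glucose disposal".

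**The concern.** Both sections credit one study with a muscle uptake difference between the hyperthyroid and euthyroid states, yet one implies 0.9 and the other states 1.4. All the Introduction's figures agree on 0.9: the two means, the fold change and the whole-muscle estimate. The 1.4 stands alone, with no derivation, units or named contrast. It may be an error, or it may be a different comparison, such as patients before and after return to euthyroidism. The document does not say.

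The SD is a second uncertainty. The 0.6 equals the SD printed for the hyperthyroid state. A paired test needs the SD of the within-subject change, and the protocol does not say that 0.6 is that quantity.

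At stake is the power claimed for a named key secondary endpoint. Muscle is the tissue that the protocol expects to take up most of the extra glucose. PET is done in adults only, entry is from age 12, and no minimum number of adults is set. A reader who trusts the figure of 4 could accept a PET subset that is too small.

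**Working it through.** **Inputs**
- Introduction: hyperthyroid 1.9 ± 0.6, euthyroid 1.0 ± 0.3 µmol/100g/min; muscle mass 30,000 g; excess 270 µmol/min.
- Sample Size Justification: difference 1.4, SD 0.6, n = 4, 80% power, two-sided alpha 0.05.
- Statistical Methods for Data Analysis: paired before/after comparison for primary and secondary outcomes.

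**Which difference the Introduction uses**
- 1.9 − 1.0 = 0.9, and 1.9 / 1.0 gives the 1.9-fold increase.
- 0.9 × 30,000 / 100 = 270 µmol/min, as printed. A difference of 1.4 would give 1.4 × 300 = 420.

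**Method**

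Exact paired t-test: with n pairs, the statistic follows a noncentral t distribution with n − 1 degrees of freedom and noncentrality (difference / SD of change) × √n. Power is the probability that it exceeds the two-sided 5% critical value.

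**Reproducing the plan's figure**
- 1.4 / 0.6 at n = 4: noncentrality 2.333 × 2 = 4.67, critical value 3.18, power 86.0%. At n = 3, power is 57.2%. So n = 4 is right for these inputs.
- All 30 cells of the muscle uptake table reproduce with this method. The formula is not in question, only the input.

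**Power by difference, at SD 0.6**

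| Difference | n = 4 | n = 5 | n = 6 | n = 7 | n = 10 |
|---|---|---|---|---|---|
| 1.4 | 86.0% | 96.7% | 99.4% | 99.9% | >99.9% |
| 1.0 (a row of the plan's table) | 61.3% | 79.3% | 89.9% | 95.3% | 99.6% |
| 0.9 | 53.3% | 71.1% | 83.3% | 90.8% | 98.7% |

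At SD 0.6, 4 pairs reach 80% power only for a difference of at least 1.28. The plan's own table requires 6 subjects for a change of 1.0 at that SD, so 4 cannot be enough for the smaller 0.9.

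**How far the result depends on the SD**

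For a difference of 0.9, the largest SD of change that keeps 80% power is 0.42 with 4 pairs, 0.54 with 5, 0.63 with 6, 0.71 with 7 and 0.90 with 10.

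If 0.6 and 0.3 are the SDs of the two states, then for a within-subject correlation r the SD of change is √(0.6² + 0.3² − 2r × 0.6 × 0.3) = √(0.45 − 0.36r). The document gives no value for r, so these are assumptions:

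| r | SD of change | Power, n = 4 | Pairs for 80% | Power, n = 10 |
|---|---|---|---|---|
| 0 | 0.67 | 45% | 7 | 96% |
| 0.25 | 0.60 | 53% | 6 | 99% |
| 0.5 | 0.52 | 64% | 5 | >99% |
| 0.75 | 0.42 | 79.8% | 5 | >99% |

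Just above r = 0.75, 4 pairs become enough (80.5% at 0.76).

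**The case against.** The strongest reply is that the power statement contains no error of its own. Its n follows from its inputs, and the cited study may well report a second contrast that gives 1.4. The Introduction mentions both a comparison with euthyroid controls and a return to normal after treatment. Without the source, one can say that the two figures differ, not that the power is too high. This stands, and the conclusion below is conditional for that reason.

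A second reply is that n = 4 does not depend on 1.4 alone. With a difference of 0.9 and state SDs of 0.6 and 0.3, 4 pairs suffice once the within-subject correlation passes about 0.75. That is correct. But it needs an SD of change of 0.42 or less, whereas the plan states 0.6, and with 0.6 the figure of 4 cannot be kept for 0.9.

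A third reply is that nothing in the design rests on n = 4. The sample size is set for the primary outcome, the table already shows less favourable cases, the protocol admits uncertainty in its calculations, and the target is at least 10 with a cap of 20. This also stands and keeps the point minor. It does not remove the contradiction, and the target of 10 counts all patients, whereas only adults are scanned.

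**Conclusion.** The point holds and is minor. The protocol attributes differences of 0.9 and 1.4 to one study without reconciling them, and its statement of 80% power with 4 subjects was derived from the 1.4.

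If 0.9 is the right contrast and 0.6 is the SD of the paired change, power at 4 subjects is 53%, against the stated 80% (86% when computed exactly from the plan's own inputs), and 6 pairs are needed. If 0.6 is instead the SD of one state, the requirement is 5 to 7 pairs for assumed correlations from 0.75 down to 0, and 4 only above that. If 1.4 proves to be the right contrast and 0.6 its paired SD, the power statement is correct and needs only an explanation.

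In every scenario computed, 10 adult pairs give at least 96% power. The recruitment target therefore covers the endpoint, provided about 6 to 7 adults complete both scans.

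**What to change.** Check the cited PET study once and reconcile the two sections. Then, according to what it shows:
- **0.9 applies:** restate the power sentence as a difference of 0.9 with SD 0.6, for which 6 adult pairs give 83% power and 4 pairs give 53%.
- **0.6 is the SD of a single state:** replace the single number with a range of 5 to 7 pairs, and state the assumed within-subject correlations (0.75 to 0).
- **1.4 is a different contrast:** name it and give the SD of its paired change.
- **1.4 is correct for the same contrast:** correct the means, the 1.9-fold figure and the 270 µmol/min in the Introduction.

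In each case, add the units and say what the SD describes. The cost is one look at the source and one reworded sentence, or a few corrected figures in the Introduction. Enrolment, endpoints and tests do not change.

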### 6 month study

The primary objective of the 6 month study is to assess the impact determine the effect of thyroid hormone on A1c over 6 months in patients with mutations of the insulin receptor who have poorly controlled diabetes. Recent data from our group in the same population (with a different intervention) indicates the A1c change 6 month after treatment is about 2.1 with standard deviation of 1.4. If we expect similar A1c changes in the current study, then a sample size of 6 will lead to a power of 80% (at a two-sided alpha of 0.05). A sample size of 7 would allow us to detect an A1c change of 2.0 with a standard deviation of 1.5.

Based on all of the above, we will endeavor to recruit at least 10 patients with this extremely rare condition into the 2 week study, and have at least 7 progress into the 6 month study. All patients who complete the 2 week study and who are eligible for the 6 month study will (if they consent) proceed immediately from the 2 week study into the 6 month study. As not all subjects may complete the study, and the sample size calculations have some uncertainty, we will cap enrollment at 20 subjects. Currently, we follow 17 patients with insulin receptor mutations, of whom 10 have poorly controlled diabetes. In addition, we are in touch with other physicians throughout the world who follow similar patients who might be interested in participating in this study.

### ***Statistical Methods for Data Analysis***

The following analyses will be performed:

- Descriptive statistics of response variables by visit. This includes calculation of means and standard deviations of the response variables at the pre and post treatment visits.
- Paired comparison of measurements before and after the treatment for primary and secondary outcomes
- Model analysis of selected response variables

#### ***Primary Response Variable***

Primary response variable for the 2 week study is change in total body glucose disposal from baseline to 2 weeks after the treatment. A paired t-test will be used to compare the glucose disposal before and after treatment. A p-value of 0.05 or less is considered significant.

The primary response variable will also be analyzed using the Linear Mixed Model (LMM). This will allow for comparison of glucose disposal at different visit adjusting for additional covariates. The potential covariates include:

- Probable covariates
  - Fasting blood glucose
  - Fasting insulin
  - T3 level
  - Lean mass
- Possible covariates
  - Age
  - Sex
  - Mutation type (dominant versus recessive)

The effect of covariates that could influence the primary response variable will be tested by including each of the covariates detailed above into a mixed model. Each model tested will only include a single covariate due to small sample size.

The primary response variable for the 6 month study is the change in A1c from baseline to 6 month after the treatment. Analyses of A1c measurements are similar to that for the primary response variable.

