#### ***Liothyronine (T3)***

T3 is the active form of thyroid hormone. Our rationale for choosing liothyronine (T3) over levothyroxine (T4) for this study is for two reasons. First, due to the short duration of the initial proof of principle study (two weeks), we would prefer to use a formulation of thyroid hormone with a short half-life that can be rapidly titrated. The half-life of liothyronine is a few hours, versus levothyroxine which is one week, thus allowing us to rapidly titrate the dose. Secondly, we prefer to use a formulation of thyroid hormone that will maximally stimulate BAT without the need for conversion from T4 to T3 by type 2 deiodinase. By using liothyronine as opposed to levothyroxine, we are able to study the direct effect of T3 on BAT, and are essentially eliminating an additional step.

Replacement doses of T3 to achieve euthyroidism in hypothyroid adults are approximately 0.57 mcg/kg/day. Stable plasma T3 levels can be achieved with q8 hour T3 dosing. In this study, the goal will be to achieve peak plasma T3 levels between 125% and 150% of the upper limit of normal (200 ng/dL in the NIH Clinical Center laboratory). The estimated T3 dose to achieve this level of plasma T3 is 2 times the replacement dose, or 1.14 mcg/kg/day. In a 50 kg individual, this equals 57 mcg. T3 is available in dosing increments of 5 mcg; thus doses will be rounded (lower dose will be used if calculated dose is 0 to <2.5 mcg above a dose divisible by 5; higher dose will be used if dose is 2.5 to <5 mcg above a dose divisible by 5). By comparison, T3 at doses of 150 mcg per day (~2.1 mcg/kg/day, or

approximately 4 times the replacement dose) was given to healthy, euthyroid adults for 2 weeks, raising plasma T3 levels from 125 to 507 ng/dL. This treatment was well tolerated, with an increase in heart rate from 65 to 78 beats per minute, and weight loss of 2 kg, and the development of “mild to moderate symptoms of enhanced appetite, nervousness, headache, or palpitations”. In a similar study, T3 at doses of 75 to 100 mcg per day (1.1 to 1.4 mcg/kg/day) was given to healthy, euthyroid adults for 2 weeks, raising plasma T3 levels from 110 to 350 (range, 190-520) ng/dL, with no reported adverse events.

The dose titration scheme for T3 is as follows:

- Day 1: 1x replacement (0.57 mcg/kg/day)
- Day 2: 1.5x replacement (0.855 mcg/kg/day)
- Days 3-14: 2x replacement (1.14 mcg/kg/day)

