Plasma T3 peak (2-4 hours, with a goal of 3 hours, after morning dose) and trough (just before morning dose) levels will be measured on a daily basis for the first week, and every other day thereafter. If the T3 peak or trough exceeds targets below, the peak and trough will be repeated the following day (or the same day at the investigators’ discretion), and doses will be reduced if trough or peak levels exceed targets on both measurements.

- Target trough T3 = 150-250 ng/dL (25% above or below the upper limit of normal of 200 ng/dL)
- Target peak T3 = 250-300 ng/dL

In addition, if subjects meet one or more of the following clinical and biochemical criteria the dose will be reduced to avoid toxicity:

- Tachycardia, defined as heart rate consistently over 110 over a 24 hour period
- Symptomatic palpitations
- Anxiety or nervousness that are not tolerable to the patient
- Development of systolic hypertension (defined as >130 mmHg AND a  $\geq$  10 mmHg increase over baseline) for a 24 hour period)
- Chest pain
- Congestive heart failure
- Diarrhea that is distressing to patient
- Weight loss > 4 kg or >10% of body weight (whichever is smaller)
- Peak T3 > 350 ng/dL

After the conclusion of the 2 week T3 treatment, subjects with poorly controlled diabetes will continue long-term (6 month) management with T3, at the maximum dose tolerated during the inpatient study (up to 1.14 mcg/kg/day). Because key safety monitoring and dose titration occur during the 2 week study, subjects must participate in the 2 week study in order to proceed to the 6 month study. During the next 6 months, doses will be reduced if the following toxicity criteria are met:

- Symptoms of thyroid hormone excess that are intolerable to the subject are reported by the patient, or elicited on monthly telephone screening, including:
  - Symptomatic palpitations (sensation of racing heart)
  - Changes in sleep, mood or behavior, school/work performance
  - Tremulousness, anxiety, sweating, diarrhea, or heat intolerance.
- Signs of thyroid hormone excess are detected at the 3 month NIH follow-up visit, including:
  - Tachycardia, defined as heart rate consistently over 110 over a 24 hour period
  - Development of systolic hypertension (defined as >130 mmHg AND a  $\geq$  10 mmHg increase over baseline) for a 24 hour period)

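### The supplementary mixed model lists T3 level as a covariate for the visit comparison; if visit-specific T3 is entered, the visit coefficient is no longer the T3 effect

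*Combined protocol and SAP*

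**What the plan says.** All references are to the combined protocol and SAP.

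- **Primary Response Variable.** The main analysis of the 2 week study is a paired t-test of glucose disposal before and after treatment, judged at 0.05. A linear mixed model is added, and its use is given as: "This will allow for comparison of glucose disposal at different visit adjusting for additional covariates". The probable covariates are fasting glucose, fasting insulin, T3 level and lean mass. The possible ones are age, sex and mutation type. Each model takes one covariate.
- The same section then gives the covariate models a second use: "The effect of covariates that could influence the primary response variable will be tested".
- For the 6 month endpoint it adds: "Analyses of A1c measurements are similar to that for the primary response variable".
- **Liothyronine (T3).** The plasma level is something the protocol sets: "the goal will be to achieve peak plasma T3 levels between 125% and 150% of the upper limit of normal". The stated targets are "Target trough T3 = 150-250 ng/dL" and "Target peak T3 = 250-300 ng/dL". Peak levels are monitored on treatment, "and trough (just before morning dose) levels will be measured on a daily basis for the first week", and every other day after that.

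The plan does not say whether the T3 covariate is a baseline or a visit-specific value, whether it is peak or trough, or which coefficient of the T3 model is to be interpreted.

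**The concern.** The only difference between the two visits that the study wants to measure is T3. A model that compares visits while holding T3 level constant asks how much disposal would change if T3 did not. That is a direct-effect question, not the study question, and T3 level and visit are strongly correlated by design.

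A report of this model could therefore show little or no T3-adjusted visit effect when T3 works, and so seem to contradict a positive paired t-test. In an uncontrolled study of about 10 patients, such an apparent disagreement would be hard to explain afterwards. Because the T3 measure is not fixed, the choice could also be made after the data are seen.

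**Working it through.** **1. The plan's own figure.** Sample Size Justification gives a change of 0.39 mg/kg/min, an SD below 0.27 (0.27 used here), two-sided alpha 0.05, and n = 6 for 80% power. A noncentral t calculation gives 80.5% at n = 6, so the figure reproduces. At the planned minimum of n = 10 the paired t-test has 98.1% power. Its expected 95% half-width is about 2.262 × 0.27/√10 = 0.19.

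**2. What the visit coefficient becomes.** Take the model y = α + subject + δ·visit + β·T3 + error. Differencing within subject gives

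change in y = δ + β·(change in T3) + error.

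The total effect is δ + β·D, where D is the mean T3 change. If a share m of the effect runs through measured T3, then β = m × 0.39/D and δ = (1 − m) × 0.39. Hence δ = 0.39, 0.195 or 0.00 for m = 0, 0.5 or 1. This does not depend on n or on the T3 SDs.

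**3. Inputs for precision.**
- Before treatment: T3 of 125 ng/dL, from healthy adults in a cited study ("raising plasma T3 levels from 125 to 507 ng/dL"), used as a proxy.
- On treatment: mid-target peak 275 or mid-target trough 200, so D = 150 or 75.
- Assumed: T3 SD 20 before; 20, 30 or 60 on treatment; values independent across visits. The SD of the T3 change is then s = √(20² + SD²) = 28.3, 36.1 or 63.2.
- The total SD of change in disposal is held at 0.27, so residual SD = √(0.27² − (m × 0.39/D)² × s²).

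**4. Collinearity.** Correlation of T3 with visit = (D/2)/√(D²/4 + s²/2). Standard-error inflation of the visit term = √(1 + nD²/((n−1)s²)). For example, peak with SD 20 gives √(1 + 10 × 22500/(9 × 800)) = √32.25 = 5.7.

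| T3 measure | On-T3 SD | Correlation with visit | SE inflation | Rejection, m = 0 |
|---|---|---|---|---|
| Peak | 20 | 0.97 | 5.7 | 11% |
| Peak | 30 | 0.95 | 4.5 | 15% |
| Peak | 60 | 0.86 | 2.7 | 32% |
| Trough | 20 | 0.88 | 3.0 | 27% |
| Trough | 30 | 0.83 | 2.4 | 38% |
| Trough | 60 | 0.64 | 1.6 | 67% |

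Rejection rates come from 20,000 simulated trials per setting, with t on 8 df.
- m = 0: the estimate averages 0.39 and the median 95% half-width is 0.31-1.11.
- m = 0.5: the estimate averages 0.19-0.20 and rejection is about 6-35%.
- m = 1: the estimate averages 0.00 and rejection is about 5%. Trough with SD 60 is left out here, because (0.39/75) × 63.2 = 0.33 exceeds 0.27.

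A random-intercept REML model (300 trials in each of 5 T3 settings, between-subject SD 0.5 assumed) agrees: rejection is 12-65% for m = 0 and 4-5% for m = 1.

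**5. A wider T3 spread.** Liothyronine (T3) also reports a study in healthy adults with T3 rising from 110 to 350 and a range of 190-520 ng/dL. If that range of 330 spans 3 to 4 SDs (assumption), the SD is about 83-110. With D = 150, SE inflation is 1.7-2.1 and rejection at m = 0 is 46-61%. With that study's own change of 350 − 110 = 240, they are 2.5-3.1 and 26-36%.

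**6. Baseline T3 instead.** It is constant within subject and cancels from the difference. In simulated complete pairs the visit estimate moved by at most 1.2e-15. In three example fits with 2 of 10 post values missing it moved by at most 0.003.

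**The case against.** The strongest reply is that the plan never says the visit coefficient of the T3 model will be reported as an adjusted T3 effect. The sentence on testing covariates fits a reading in which the T3 coefficient is what matters, and that coefficient is a legitimate exposure-response slope. The covariate list supports this. Age, sex and mutation type are fixed or nearly fixed over 2 weeks, so as main effects they cannot change a complete-pair visit contrast either, and they make sense mainly as tests of covariates. This stands as a reason for calling the wording ambiguous. It does not remove the point, because the visit comparison with adjustment is a stated use of the model, T3 level is on the list, and nothing excludes it from that comparison.

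It is also fair that the T3 SDs and mediation shares are not in the documents, and that the wider spread in step 5 gives milder losses. Dose reduction above target could narrow the spread again, so no single rejection rate is established. The change in what δ estimates does not depend on the SDs.

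Finally, one sentence naming the coefficient to be interpreted would go most of the way. That is true: the intercept and the slope come from the same regression.

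**Conclusion.** The point holds and is minor. With visit-specific T3, the visit coefficient does not estimate the T3 effect. It averages about half the true change if half the effect runs through measured T3, and zero if all does. If none does, it is unbiased but much less precise than the paired comparison in most settings tried. The attenuation rests on the assumed share; the loss of precision rests on the assumed T3 SDs and on a proxy baseline.

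A reader might infer more than the documents support:
- *That the primary result is at risk.* It is not. The 0.05 criterion is attached to the paired t-test, the sample size is built on the paired change, and no stated decision uses the mixed model.
- *That baseline T3 would also be a fault.* Entered as a main effect it is harmless; it simply adjusts nothing in complete pairs.
- *That every secondary outcome is affected.* Secondary Response Variables asks for a similar manner of analysis, but Statistical Methods for Data Analysis limits modelling to selected response variables. The carry-over to A1c is explicit; beyond that it reaches only the outcomes chosen for modelling.
- *That on-treatment fasting glucose, fasting insulin or lean mass biases the comparison in the same way.* Their timing is unstated, but the documents give neither direction nor amount, so this is missing detail and not part of the point.

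**What to change.** In Primary Response Variable:
1. Remove T3 level from the model used for the visit comparison.
2. State that the T3 effect is taken from the paired t-test, or from a mixed model without on-treatment T3.
3. Report change in outcome against change in T3 as a separate exploratory exposure-response analysis with its confidence interval, and name peak or trough in advance. For the 6 month part, the monthly safety labs in Study Procedures specify trough T3.
4. Apply the same wording to A1c and to any secondary outcome selected for modelling.

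The cost is SAP wording only; T3 and the outcomes are already collected. The T3-adjusted visit comparison would no longer be reported. The slope that replaces it is imprecise at n = 10: even if the whole effect runs through T3, its power is about 12%, 17% and 50% for peak (on-T3 SD 20, 30, 60) and about 39% and 66% for trough (SD 20, 30). A non-significant slope should therefore not be read as absence of an exposure-response relation.
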